7. TIMELINE

Based on the present design and assessment of our center's patient population with CLAD, we estimate the study duration will be 2 years. Patient enrollment can start as soon as regulatory agency approval is obtained (IRB). We have experienced clinical coordinators in our transplant center. [name], the clinical coordinator for the trial, has conducted lung transplant studies with [name] for nearly a decade. [name] and [name] are both transplant pulmonologists and are committed to this trial. [name] Sc.D. is an experienced biostatistician whose area of expertise is clinical trials and she has worked extensively with lung transplant cohorts. In summary, all infrastructure is already in place allowing for rapid start of the proposed clinical trial.

8. DRUG DOSAGE & ADMINISTRATION

Dosage and Administration

	Pirfenidone	Placebo
Substance	Pirfenidone	-
Pharmaceutical formulation	Capsule	Capsule
Source	Genentech	Genentech
Unit strength	267 mg	267 mg
Route	Oral	Oral
Dosage		
Days 1 through 7	267 mg three times daily	267 mg three times daily
Days 8 through14	534 mg three times daily	534 mg three times daily
Days 15 onward	801 mg three times daily	801 mg three times daily

- Take with food.
- Upon initiation of treatment, titrate to the full dosage of 2403 mg/day over a 14-day period as above.

8.1 Adverse reactions

The most common adverse reactions (≥10%) are liver problems, photosensitivity, rash, abdominal pain, nausea, vomiting, diarrhea, dyspepsia, fatigue, headache, dizziness, anorexia, sinusitis, insomnia, weight loss, and arthralgia. These possible adverse events are documented in the informed consent.

Management of abnormal liver function tests

Elevated ALT, AST, and bilirubin elevations have occurred with pirfenidone and will be monitored monthly as above. The investigator will monitor patients for toxicities.

The following protocol will be followed for management of elevation in AST, ALT, and total bilirubin:

Magnitude of AST or ALT elevation	Recommendation
3 to 5 x ULN	Confounding medications should be discontinued if clinically indicated, other causes excluded, and the patient monitored closely. The dose of study treatment may be reduced or interrupted if clinically appropriate, with subsequent repeat titration to full dose, as tolerated
≤5 x ULN accompanied by symptoms or hyperbilirubinemia (>2x ULN)	Study treatment should be permanently discontinued
>5 x ULN	Study treatment should be permanently discontinued

Management of photosensitivity and rash

Photosensitivity and rash have been noted with pirfenidone. Patients will be instructed to avoid exposure to sunlight and sunlamps. Patients will be instructed to wear sunscreen (sun

protection factor 50 or higher) and protective clothing daily. Temporary dosage reductions or discontinuations may be required.

If a patient experiences significant rash or photosensitivity, treatment of symptoms and/or temporary dose reductions, interruptions, or discontinuation of study treatment should be considered.

Management of gastrointestinal disorders

Nausea, vomiting, diarrhea, dyspepsia, gastroesophageal reflux disease, and abdominal pain have occurred with pirfenidone. Temporary dosage reductions or discontinuations may be required.

Dosage Modification due to Drug Interactions

Ciprofloxacin is a moderate CYP1A2 inhibitor. With the use of ciprofloxacin at a dosage of 750 mg twice daily, reduce pirfenidone to 534 mg three times a day (1602 mg/day).

EKG abnormalities

If the QTc interval is > 550 msec, this should be confirmed with a repeat EKG within 24 hours. The study drug should be interrupted until the repeat EKG reading. If QTc is still >550 msec than cardiology will be consulted and drug discontinued if abnormality persists.

If the QTc interval is between 500 and 550 msc, confirmed by a repeat EKG within 24 hours, and verified by a local cardiologist, study treatment should be interrupted. If an alternative explanation is identified (electrolyte abnormality or concomitant medication), the study treatment may be re-initiated at the investigator's discretion in consultation with the medical monitor.

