4.4 EXCLUSION CRITERIA

- Acute Rejection (AR) diagnosis by biopsy in the 28 days prior to enrollment
- Treatment with pulse steroids, Anti-thymocyte Globulin (ATG), extracorporeal photopheresis (ECP), plasmapheresis, or Immunoglobulin therapy aimed at CLAD within the 28 days prior to enrollment
- If the subject is receiving chronic Azithromycin therapy, the dose must be stable for the 28 days prior to enrollment
- Presence of active pulmonary infection at the time of enrollment as determined by an investigator in consultation with the treating pulmonologist
- Diagnosis of bronchial stenosis either a) requiring stenting, or b) thought to be responsible for the spirometric decline by principal investigator
- Abnormal liver function tests (AST or ALT > 2 x upper limit of normal (ULN), Alkaline phosphatase > 2.5 x ULN, total bilirubin > ULN) or known cirrhosis (>2 times upper limit of normal of AST/ALT/AP)
- Total WBC < 3.0 K/uL
- Moderate to Severe Renal insufficiency (CrCl <15 mL/min calculated by the Cockcroft-Gault equation)

- Use of any medication known to cause significant interactions with pirfenidone (strong CYP1A2 inhibitors such as Fluvoxamine or Enoxacin or inducers)
- Pregnancy or lactation. Women of child-bearing potential will have a pregnancy test at enrollment and must agree to maintain highly effective contraception with two methods of birth control from the date of consent through the end of the study.
- Tobacco use within 6 months
- History of alcohol abuse in the past 1 year as determined by the treating pulmonologist
- Any condition other than CLAD that will likely result in death in the next 1 year
- Any condition in the judgement of the principal investigator that would preclude participation in this study
- EKG with QTc interval > 500 msec at screening
- Listed for repeat lung transplantation

Excluded therapies:

The following therapies are not permitted during the study:

- Investigational therapy, enrollment in another therapeutic clinical trial within 30 days or 5 half-lives of study medication (whichever is longer)
- Fluvoxamine

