10.3 Primary Endpoint Analysis

We believe the data obtained from our study will provide important radiographic and biological signals regarding the efficacy of pirfenidone. We expect a lower SD as the patient population selected will be much better phenotyped for CLAD presence. The high SD in the preliminary data came from patients who improved over time as this data is derived from patients who had CT scans available as routine care rather than in our study where they will be done prospectively. Furthermore, if fibrotic remodeling by pirfenidone is effective we can potentially even see a decrease in fSAD.

We believe that this CT based novel methodology to evaluate small airway disease will provide us with much stronger signal over 6-month period than FEV1 which reaches a floor effect. So the disease progresses even though FEV1 changes are not very evident ultimately leading to graft failure and death. Furthermore, our ability to isolate mesenchymal cells from BAL offers a first unique scenario to directly study the anti-fibrotic effect of pirfenidone.

This trial will also provide information regarding the tolerance of pirfenidone in a lung transplant population who already take multiple medications with serious possible side effects. Tolerance of pirfenidone in addition to baseline transplant medications will be assessed.

Secondary:

- Change in FEV₁ over 24 weeks by treatment arm (e.g, percent or time weighte)
- Change in FVC over 24 weeks by treatment arm
- Number of subjects with treatment intolerance over 24 weeks
 - Measured by elevated AST, ALT, total bilirubin that results in dose reduction or discontinuing study treatment (the 3 – 5 or greater ULN)
- Number of subjects with Adverse events related to treatment with Pirfenidone
 - Safety of pirfenidone will be measured by adverse events determined to be related to the study drug as determined by the principal investigator through

review of medical history, physical exam and laboratory findings *or be measured by liver and renal function tests, physical exam*

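### Row 2 of the liver table in section 8.1 has no lower AST/ALT bound on its symptom limb, so read literally it recommends a permanent stop for nausea at 1.8 x ULN

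*Combined protocol and SAP*

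**What the plan says.** Section 8.1 introduces its liver table with "The following protocol will be followed for management of elevation in AST, ALT, and total bilirubin". The bands refer to the size of an AST or ALT elevation, and the action column is headed as a recommendation.

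- Row 1 covers 3 to 5 x ULN. Its action includes: "The dose of study treatment may be reduced or interrupted if clinically appropriate, with subsequent repeat titration to full dose, as tolerated".
- Row 2 covers "≤5 x ULN accompanied by symptoms or hyperbilirubinemia (>2x ULN". Its action is permanent discontinuation.
- Row 3 covers values above 5 x ULN, with the same action as row 2.

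The same section lists common reactions: "The most common adverse reactions (≥10%) are liver problems, photosensitivity, rash, abdominal pain, nausea, vomiting, diarrhea, dyspepsia, fatigue, headache, dizziness", and others. Its gastrointestinal paragraph reads: "Nausea, vomiting, diarrhea, dyspepsia, gastroesophageal reflux disease, and abdominal pain have occurred with pirfenidone. Temporary dosage reductions or discontinuations may be required". For significant rash or photosensitivity, "temporary dose reductions, interruptions, or discontinuation of study treatment should be considered".

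On liver tests, section 4.4 excludes patients with "AST or ALT > 2 x upper limit of normal (ULN), Alkaline phosphatase > 2.5 x ULN, total bilirubin > ULN", or with known cirrhosis.

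**The concern.** Row 1 starts at 3 x ULN and row 3 starts above 5 x ULN. Row 2 has only an upper limit, and nothing in the row says which symptoms count. Nowhere else does the protocol supply a floor for row 2 or restrict its symptoms to hepatic ones.

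The symptom limb therefore reaches mild elevations that 4.4 accepts at entry, and it can be met by a complaint that 8.1 lists among the drug's common reactions. A patient with a tolerated, stable elevation could be taken off study drug for good because of an event that a later paragraph of 8.1 lets the investigator manage by a temporary change. Two investigators following the same page could treat the same patient differently. What is at stake is unnecessary loss of exposure to study drug and inconsistent handling of individual patients.

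**Working it through.** The plan gives no figure to reproduce here. The check applies the printed rows to specific patients.

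**Inputs**
- Entry limit (4.4): AST or ALT above 2 x ULN is excluded. Since 1.8 ≤ 2, a patient at 1.8 x ULN is eligible on this criterion.
- Row 1 (8.1): 3 ≤ AST/ALT ≤ 5 x ULN.
- Row 2 (8.1): AST/ALT ≤ 5 x ULN, and either symptoms or bilirubin > 2 x ULN.
- Row 3 (8.1): AST/ALT > 5 x ULN.
- The column header speaks of an elevation, so only values above ULN are considered. 1.8 x ULN is above ULN.

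**Rows met, with bilirubin ≤ 2 x ULN**

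| AST/ALT (x ULN) | Symptoms | As printed | Row 2 symptom limb floored at 3 x ULN |
|---|---|---|---|
| 1.8 | none | no row | no row |
| 1.8 | nausea | row 2: permanent stop | no row; gastrointestinal paragraph applies |
| 2.9 | nausea | row 2: permanent stop | no row; gastrointestinal paragraph applies |
| 4 | none | row 1 | row 1 |
| 4 | nausea | rows 1 and 2 | row 2, by stated precedence |
| 5.1 | any | row 3 | row 3 |

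2.9 x ULN could not be an entry value, because 2.9 > 2, but it could arise on treatment.

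**The example step by step**
1. At 1.8 x ULN, row 1 does not apply (1.8 < 3) and row 3 does not apply (1.8 < 5).
2. Row 2 does apply: 1.8 ≤ 5, and nausea is a symptom.
3. The liver table therefore points to a permanent stop, while the gastrointestinal paragraph names nausea and allows a temporary reduction or discontinuation.

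**What a plain floor would lose.** Putting a floor of 3 x ULN on the whole of row 2 would also remove the stop for bilirubin above 2 x ULN at, say, 2.9 x ULN. It would likewise remove the stop for jaundice or asterixis below 3 x ULN. Section 11.3.2(a) gives jaundice and asterixis as examples of manifestations of liver failure or hepatitis. The floor should therefore apply only to symptoms that are not signs of liver injury.

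**The case against.** The strongest reply is that no sensible reader would apply row 2 this way. The table stands under a heading on abnormal liver tests, its actions are recommendations phrased with 'should', and the symptoms must accompany an elevation. In the example the enzymes have not moved since entry. The gastrointestinal paragraph deals with nausea by name and would ordinarily govern. Most of this stands: the permanent stop is the literal outcome, not a certain one, and row 2 was probably written as the exception to row 1. But that intent depends on a lower bound that is not printed, and the lead-in says the table will be followed.

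Three stronger readings are tempting, and the documents do not support them.

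- *Rows 1 and 2 contradict each other at 3 to 5 x ULN.* Row 1 is permissive, while row 2 adds a condition and a firmer action. This is ordinary general rule and exception. A statement of precedence is enough.
- *The intolerance measure in 10.3 wrongly misses such a stop.* That measure counts "elevated AST, ALT, total bilirubin that results in dose reduction or discontinuing study treatment (the 3 – 5 or greater ULN". A stop prompted by nausea with stable enzymes does not result from an enzyme elevation, so leaving it out of a liver measure is consistent. The permanent-discontinuation count in 10.1 captures it.
- *The rule would stop more patients on pirfenidone than on placebo.* The documents give neither the share of patients expected to enter above ULN nor reaction rates by arm, so no difference can be claimed.

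**Conclusion.** The point holds as a minor defect in an operational rule: the symptom limb of row 2 lacks a lower AST/ALT bound, and its literal result conflicts with another paragraph of 8.1. Confidence is high about the printed wording, and lower about how often, if ever, anyone would act on the literal reading.

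The number of patients affected cannot be estimated from the documents, and none is assumed. The consequences are limited in any case. Under 5.7, patients who stop study drug are asked to continue assessments through the week-24 HRCT, so the primary endpoint can still be collected. Under 10.1, every permanent stop before week 24 is counted.

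The conclusion assumes that the table row is complete as printed and that 'symptoms' carries its ordinary meaning. If the sponsor confirms that row 2 was always meant to start at 3 x ULN, the defect is one of wording only, and the same edit resolves it.

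**What to change.** Reword row 2 along these lines: AST/ALT 3 to 5 x ULN with symptoms, or any AST/ALT elevation up to 5 x ULN with total bilirubin >2 x ULN or with signs of liver injury such as jaundice or asterixis: permanently discontinue. State that row 2 takes precedence over row 1. Leave rows 1 and 3 unchanged.

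Add one sentence: below 3 x ULN, with bilirubin ≤2 x ULN and only non-hepatic symptoms, manage under the gastrointestinal or rash paragraphs with close enzyme monitoring.

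No change to 10.1 or 10.3 is needed, and the stop for symptoms at 3 to 5 x ULN should not be relaxed.

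The cost is a short edit to one table. The downside is that the printed stop is loosened for non-hepatic symptoms below 3 x ULN, and only there. The clinical team must confirm that 3 x ULN is the right bound.

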9. DRUG STORAGE & HANDLING

Pirfenidone capsules and film-coated tablets are packaged in high-density polythylene bottles with a child-resistant closure system.

Hard capsules should be stored under the recommended storage conditions "Do not store above 30 degrees C". Film-coated tablets should be stored under the recommended storage condition "Do not store above 25 degrees C".

For batch specific instructions on storage and information on shelf-life, see the packaging.

The Michigan Medicine Research Pharmacy is responsible for developing and implementing procedures for the proper control and handling of investigational drugs, including procurement, storage, medication labeling and dispensing, drug inventory management, and other distribution and control functions. Information on a drug accountability log includes but is not limited to: receipt date, dispensation date, patient identifier, quantity, lot number, expiration date, and dispenser's initials. Appropriate inventory levels will be maintained by RP to ensure availability of study drugs. As indicated by the sponsor, outdated study medications will be returned by RP to the study sponsor or destroyed.

Drug shipping information: University of Michigan Hospitals Department of Pharmacy Services-Research Pharmacy [name]

[contact]

10. DATA ANALYSIS

10.1 Overview

Our Endpoints are:

Primary:

- Change in functional small airways disease (fSAD) as measured by parametric response mapping (PRM) at 24 weeks by treatment arm

Secondary:

- Change in FEV₁ over 24 weeks by treatment arm
- Change in FVC over 24 weeks by treatment arm
- Number of subjects permanently discontinuing study medication before 24 weeks
- Number of subjects with one or more serious adverse events

Exploratory:

- Change in bronchoalveolar lavage (BAL) mesenchymal colony forming units (CFUs) by treatment arm
- Change in fibrotic phenotype of BAL mesenchymal cells (expression of collagen, alpha smooth muscle actin, beta-catenin, fibronectin) by treatment arm

10.2 Sample Size Justification

We will describe the distribution of fSAD change within and between treatment groups (n=30 per group) over a 6-month period. Preliminary data suggests that without treatment, fSAD increases 9% on average over a 6-month time period with SD of 9%. If pirfenidone halves this increase over 6 months, we would have a confidence interval for the treatment effect of 4.5+/-4.64%. Power to detect 6-month treatment differences is sensitive to assumptions of the standard deviation above and the ability of pirfenidone to reduce 6-month fSAD progression; a power analysis table is given below for various effect sizes and standard deviations that might be seen in the trial based on a sample size of 60 (30 per group).

	% Increase in FSAD for Pirfenidone Group (vs 9% FSAD increase in Placebo Group)			
Std Dev	0%	2%	4.5%	
5	>99%	>99%	93%	
7	>99%	97%	69%	
9	97%	84%	48%	

We will similarly summarize changes in spirometric parameters and MSC CFU and phenotype over time between and within groups.

While the above power is shown with 60 patients (30 per group), we will plan to enroll 66 patients (33 per group) to account for subject drop out.

10.3 Primary Endpoint Analysis

We believe the data obtained from our study will provide important radiographic and biological signals regarding the efficacy of pirfenidone. We expect a lower SD as the patient population selected will be much better phenotyped for CLAD presence. The high SD in the preliminary data came from patients who improved over time as this data is derived from patients who had CT scans available as routine care rather than in our study where they will be done prospectively. Furthermore, if fibrotic remodeling by pirfenidone is effective we can potentially even see a decrease in fSAD.

We believe that this CT based novel methodology to evaluate small airway disease will provide us with much stronger signal over 6-month period than FEV1 which reaches a floor effect. So the disease progresses even though FEV1 changes are not very evident ultimately leading to graft failure and death. Furthermore, our ability to isolate mesenchymal cells from BAL offers a first unique scenario to directly study the anti-fibrotic effect of pirfenidone.

This trial will also provide information regarding the tolerance of pirfenidone in a lung transplant population who already take multiple medications with serious possible side effects. Tolerance of pirfenidone in addition to baseline transplant medications will be assessed.

Secondary:

- Change in FEV₁ over 24 weeks by treatment arm (e.g, percent or time weighte)
- Change in FVC over 24 weeks by treatment arm
- Number of subjects with treatment intolerance over 24 weeks
 - Measured by elevated AST, ALT, total bilirubin that results in dose reduction or discontinuing study treatment (the 3 – 5 or greater ULN)
- Number of subjects with Adverse events related to treatment with Pirfenidone
 - Safety of pirfenidone will be measured by adverse events determined to be related to the study drug as determined by the principal investigator through

review of medical history, physical exam and laboratory findings *or be measured by liver and renal function tests, physical exam*

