4.2 STUDY DESIGN

Single center, randomized, double-blind placebo controlled clinical trial of pirfenidone for the attenuation of progression of fSAD in lung transplant recipients with CLAD. A total of 60 patients will be enrolled in the trial.

Eligible patients will be randomized 1:1 to receive either pirfenidone 801 mg TID or placebo.

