4.3 INCLUSION CRITERIA

- Lung transplant recipients 18 years of age or older.
- Greater than 6 months after single or bilateral lung transplantation
- Baseline FEV₁ and FVC values (mean of two highest value measured 3 weeks apart) > 50% predicted (to assure viable graft)
- Diagnosis of CLAD (two consecutive spirometric values of FEV₁ alone or both FEV₁ and FVC < 80% of baseline)

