5.2 Baseline Assessment (Visit 1, Week 0)

At the time of baseline, the coordinator will document the following:

- Vital signs (weight, temperature, blood pressure, heart rate, respiratory rate, pulse oximetry)
- Physical exam including general appearance, HEENT, cardiovascular, pulmonary, abdominal, neurologic, dermatologic, and musculoskeletal exams
- Current medications
- Safety blood work for renal and liver evaluation
 - AST, ALT, AP, total bilirubin, creatinine
- Review bronchoscopy results (if performed)
- ECG
- Perform spirometry
- Undergo an HRCT scan with inspiratory and expiratory image acquisition (if HRCT was not done in preceding 6 weeks)
- Serum pregnancy test (if applicable)
- Review adverse events

5.3 Visits 2, 3, 5, 6 (Weeks 4, 8, 16, 20): may be performed at study center or by local lab draw in conjunction with phone visit

- Safety labs to monitor renal and liver function AP, ALT, AST, total bilirubin, creatinine
- Review hospitalizations
- Review medication compliance
- Review concomitant medications
- Review adverse events

5.4 Visit 4 (Week 12):

- Vital Signs (weight, temperature, blood pressure, heart rate, respiratory rate, pulse oximetry)
- Physical exam including general appearance, HEENT, cardiovascular, pulmonary, abdominal, neurologic, dermatologic, and musculoskeletal exams
- Safety blood work for renal and liver evaluation
 - o AP, ALT, AST, total bilirubin, creatinine
- Spirometry
- ECG
- Review hospitalizations
- Review medication adherence
- Review concomitant medications
- Review adverse events
- 5.5 Visit 7 (Week 24):
 - Vital Signs (weight, temperature, blood pressure, heart rate, respiratory rate, pulse oximetry)
 - Physical exam including general appearance, HEENT, cardiovascular, pulmonary, abdominal, neurologic, dermatologic, and musculoskeletal exams Safety blood work for renal and liver evaluation

- o AP, ALT, AST, total bilirubin, creatinine
- Spirometry
- ECG
- HRCT scan
- Review hospitalizations
- Review medication adherence
- Review concomitant medications
- Review adverse events
- Collect unused study medication and return to investigational pharmacy
- Bronchoscopy with consent of patient and primary physician if no contraindication identified

5.6 Visit 8 (Week 28) (Phone visit):

At the 28 week phone visit, the coordinator will:

- Review hospitalizations
- Review adverse events
- Collect vital status

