5.8 Randomization

This is a randomized, double-blind, placebo-controlled multi-center study. Assignment to study treatment will be blinded to the study subjects, investigational site personnel, study vendors, and the Sponsor study team, except for the delegated personnel who will review and check the randomization and drug allocation for accuracy.

All patients will be randomized at the Baseline visit, using stratified block randomization with undisclosed block sizes. The stratification factor is FEV1 first vs concurrent FEV1 and FVC decline at time of CLAD onset. Our statistician, [name], will assist with randomization. She will provide the Research Pharmacy (via email) with randomization codes for two separate strata as mentioned above. Within each stratum the statistician will indicate treatment assignment"Active Pirfenidone" or "Placebo" and treatment label ID number. The Research Pharmacist (RP) will be told upon patient entry the stratum to which the patient belongs, identifying the appropriate randomization list for each patient. The RP will then dispense Active or Placebo based on the randomization code on the randomization list. The RP will refer to the randomization code at each dispensing.

In the event of a medical emergency in which breaking the blind is required to provide medical care to the subject, the investigator may obtain treatment assignment directly from the study statistician for that subject.

Visit	Screening ^A	1 Baseline	2 ^B +/- 7days	3 ^B +/- 7days	4 +/- 14day	5 ^B +/- 7days	6 ^B +/- 7days	7 EOT +/-	8 EOS +/-
					S			14day s	7days
Week	-6 - 0	0	4	8	12	16	20	24	28 ^c
Inclusion/exclusion criteria	х								
Informed consent	Х								
Randomization		Х							
Demographics	Х								
Vital Signs	Х	Х			Х			х	
Physical exam	Х	Х			Х			х	
Medical history	х	х							
Adverse events	х	х	Х	х	х	х	х	х	х
Non-elective hospitalizations		х	x	x	x	х	х	х	x
Medication Compliance			Х	х	х	х	х	х	
Concomitant medications	X	x	х	x	x	х	x	х	
Pregnancy test ^D		Х							
Standard of care labs	x	x	х	х	х	х	х	х	
including									
immunosuppressive									
drug levels									
Safety labs (LFTs) ^F	Х	Х	Х	Х	Х	Х	Х	Х	
Spirometry	Х				Х				
Full PFTs		Х						Х	
HRCT ^G		Х						Х	
EKG		Х			Х			Х	
Bronchoscopy with BAL ^H	x	x						х	
Vital status assessment									х

Table 1. Schedule of Assessments

A The time period between the screening and enrollment visit may be up to 6 weeks

B Weeks 4, 8, 16, 20: Laboratory testing may be performed locally

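### The FEV1 measure is given only by examples and FVC has none: prespecify one week-24 contrast for both, adjusted for week-0 value and stratum

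*Combined protocol and SAP*

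**What the plan says.** Aim 2 asks whether pirfenidone stabilises FEV1 and FVC, and section 2 makes lung function decline part of the principal hypothesis. Sections 4.1 and 10.1 list change in FEV1 and change in FVC over 24 weeks by treatment arm as secondary endpoints, without a definition. Section 10.3 repeats them and adds to the FEV1 line only the parenthesis "e.g, percent or time weighte". The FVC line has no such addition.

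The only statement of method for spirometry is in section 10.2: "We will similarly summarize changes in spirometric parameters and MSC CFU and phenotype over time between and within groups". No model, covariate, time point, alpha or missing-data rule is given for these endpoints.

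Three design facts bear on the point:

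- Spirometry is listed at Visit 1 (section 5.2: "Perform spirometry"), at week 12 (section 5.4) and at week 24 (section 5.5).
- Section 5.8 stratifies the randomisation by type of spirometric decline: "The stratification factor is FEV1 first vs concurrent FEV1 and FVC decline at time of CLAD onset". No stated analysis uses that factor.
- The word baseline has two meanings. In section 4.3 it is a post-transplant reference value ("mean of two highest value measured 3 weeks apart"). In section 5.2 it is the week-0 visit.

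**The concern.** Percent change and time-weighted change are different quantities. Percent change needs a denominator, and the protocol offers two candidate baselines. Time-weighted change averages over follow-up and so gives weight to week 12. Because the two are introduced as examples, the list is open, and the choice could be made once results are known. If the more favourable result were then reported as the Aim 2 finding, its nominal error rate would be too low.

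The second matter is precision. The comparison as described is of change by arm. Left unadjusted, it gives up information already collected: the week-0 value and the stratum, which is itself defined by FEV1 and FVC decline. With about 30 patients per arm, that loss is worth avoiding.

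**Working it through.** **The plan's own figure.** The documents give no power, SD or correlation for FEV1 or FVC, so there is no spirometry figure to reproduce. The only power figures, in section 10.2, concern fSAD. With 30 per arm, SD 9 and a difference of 4.5, a two-sided 5% t-test on 58 degrees of freedom gives 47.8%, against 48% stated. A one-sided test gives 61.5%, which does not match. Two-sided 5% is therefore a reasonable assumption below, although the plan does not state it.

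**Inputs that must be assumed.** These are the correlation between the two candidate measures (0.8 to 0.95), the correlation of week-0 with week-24 FEV1 (0.7 to 0.9) and equal variance at each visit. None comes from the documents.

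**Step 1: choosing the better of two measures.** Under no effect, treat the two test statistics as bivariate normal with correlation ρ. Type I error is 1 − P(|Z₁| < 1.96 and |Z₂| < 1.96).

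- ρ = 0.80: 7.8%
- ρ = 0.95: 6.5%
- independent measures, as an upper bound: 1 − 0.95² = 9.75%

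As a check on the assumed ρ, take visit correlations of 0.7 to 0.95. Week-24 change and a trapezoid time-weighted change then correlate 0.76 under compound symmetry and 0.86 to 0.89 under AR(1). The 0.95 end is thus higher than either structure gives, and a lower correlation means more inflation. A null simulation used 20,000 trials per setting, 30 per arm, an assumed FEV1 mean of 1.8 L and SD of 0.55 L, and visit correlations of 0.8 to 0.95. Taking the better of percent change at week 24 and time-weighted change gave 6.8% to 8.4%. Taking the best of four versions (absolute or percent, week 24 or time-weighted) gave about 9% to 10%.

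**Step 2: adjusting for baseline.** With equal variances σ² and correlation r, a change score has variance 2σ²(1 − r) and a baseline-adjusted value has σ²(1 − r²). The ratio is (1 − r²) / [2(1 − r)] = (1 + r)/2.

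- r = 0.7: 0.85, a 15% cut
- r = 0.8: 0.90, a 10% cut
- r = 0.9: 0.95, a 5% cut

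As power, Φ[(1.96 + 0.84)/√ratio − 1.96]: a comparison with 80% power unadjusted would have about 86% at a ratio of 0.85 and 82% at 0.95.

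**Step 3: what week 12 adds to the week-24 contrast.** With complete data and an unstructured covariance, it adds nothing. With a fraction f missing at week 24, the variance falls by about f × R², where R² is the partial R² of week 24 on week 12 given week 0. Section 10.2 enrols 66 to keep 60, so f = 6/66 = 9.1%.

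- Compound symmetry, r = 0.7: R² = [r/(1 + r)]² = 0.170, and 0.091 × 0.170 = 1.5%
- AR(1), adjacent-visit r = 0.95: R² = r²/(1 + r²) = 0.474, and 0.091 × 0.474 = 4.3%

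Most of the gain in precision therefore comes from baseline adjustment.

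**The case against.** The strongest reply is that FEV1 and FVC are secondary, that section 10.2 speaks of summarising them, and that section 10.3 expects FEV1 to hit a floor effect. The plan states no 5% test of FEV1, so no stated error rate is breached. This stands, and it limits the weight of Step 1. It does not remove the point, since Aim 2 and the principal hypothesis ask for a treatment comparison on these measures.

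A reader might also infer more than the documents support:

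- *That week-12 spirometry is thrown away.* Only a percent change to week 24 alone would ignore it. The time-weighted option uses it, and so could a summary over time.
- *That patients without week-24 spirometry are dropped.* No missing-data rule for spirometry is stated. Section 5.7 asks patients who stop treatment to continue with assessments, and section 10.2 adds six patients for dropout.
- *That the plan commits to an unadjusted change score.* It names outcome measures and states no model. Baseline adjustment is absent but not excluded, so the 15% to 5% is a gain over an unadjusted analysis, which the plan permits without prescribing.

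A further fair objection is that the choice between litres and percent is a judgement, particularly with single and bilateral recipients both eligible, and that a week-24 contrast is narrower than change over 24 weeks. Both are choices for the investigators. What matters is that they be made in advance.

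**Conclusion.** The point holds as a minor one. The FEV1 measure is fixed only by open-ended examples, FVC has no measure, and neither the week-0 value nor the stratum enters any stated comparison. If the better of two measures were reported at a two-sided 5% level, type I error would be about 7.8% to 6.5% at an assumed correlation of 0.8 to 0.95. Baseline adjustment would cut the variance of the week-24 difference by about 15% to 5% at an assumed baseline-to-week-24 correlation of 0.7 to 0.9. Week 12 contributes little to that contrast, about 1.5% to 4.3% of variance with 9.1% missing at week 24. The documents do not show that a selective choice was intended, or that data would be discarded.

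**What to change.** Replace the parenthesis in section 10.3 with one analysis that applies to both FEV1 and FVC:

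- a repeated-measures model of the week-12 and week-24 values, on one stated scale, with an unstructured covariance;
- covariates: the week-0 value, randomisation stratum, visit, arm and arm-by-visit;
- baseline defined as the Visit 1 measurement, not the post-transplant reference value in section 4.3;
- the week-24 difference between arms, with its confidence interval, as the single named contrast;
- percent or time-weighted change reported as supportive only;
- a sentence on how deaths and missing spirometry are handled.

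The cost is a change of wording and slightly more analysis work. All the measurements are already scheduled. The one real concession is that the investigators commit to a measure in advance. If they prefer an average over weeks 12 and 24, they can name that contrast instead, but it is a different estimand and should be stated as such.
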